8.1.2 Planned Analysis

All randomized subjects who received study medication will be evaluated for safety. The efficacy analysis will be conducted on both the PP and the mITT subject populations. Two-sided hypothesis testing will be conducted for tests. Resulting p-values less than or equal to 0.05 will be considered statistically significant. No adjustments of p-values for multiple comparisons will be made. No interim analyses are planned. SAS software will be used for all data analyses and tabulations.

The treatment response will be summarized by treatment group for the end-of-treatment evaluation. The two primary efficacy endpoints will be the mean percent change from baseline to Week 12 in the inflammatory (papules and pustules) lesion counts AND the mean percent change from baseline to Week 12 in the non-inflammatory (open and closed) lesions.

8.1.3 Sample Size Considerations

Page 32 of 52

8.1.4 Efficacy Measures and Analysis

Clinical endpoints

The primary efficacy measure will be the mean percent change from baseline to Week 12 in the inflammatory (papules and pustules) lesion counts AND the mean percent change from baseline to Week 12 in the non-inflammatory (open and closed) lesion counts. The secondary efficacy measure will be the proportion of subjects with clinical success on the Investigator's Global Assessment (IGA) at Week 12. Success is defined as an IGA score that is at least 2 grades less than the baseline assessment.

Equivalent efficacy

For the mean percent reduction from baseline in the inflammatory and non-inflammatory lesion counts, the Test treatment will be considered to be therapeutically equivalent to the Reference treatment if the 90% confidence interval on the Test-to-Reference ratio of means, calculated by Fieller's Method, falls within the interval 0.80 to 1.25. The treatment means and estimate of residual variance for the confidence interval calculation will come from an Analysis of Variance of the Test and Reference results using a statistical model containing terms for Treatment and Center.

For the proportion of subjects with clinical success, the Test treatment will be considered to be therapeutically equivalent to the Reference treatment if the 90% confidence interval on the difference between Test and the Reference proportions is contained within the interval -20% to +20%. The confidence interval will be constructed using Wald's method with Yates' continuity correction.

[REDACTED]

Superiority

For the percent reductions from baseline in the inflammatory and non-inflammatory lesion counts, each active treatment will be evaluated to determine if it has superior efficacy to that of the Vehicle at Visit 4/Week 12 via an Analysis of Variance using a statistical model containing terms for Treatment and Center.

The proportion of subjects with clinical success for each active treatment will be compared to that of the Vehicle using a Z-test with Yates' continuity correction.

All hypothesis tests will be two-sided at a significance level of $\alpha = 0.05$, except confidence intervals which will be based on $\alpha = 0.1$ (i.e. 90% coverage). [REDACTED]

[REDACTED]

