5.9.1 Inflammatory Lesion Count

The numbers of facial papules and pustules, located above the jaw line to the hairline including those present on the nose, are to be counted at baseline and at each subsequent visit. The type and number of each lesion is to be recorded on the source document at each visit and the total count recorded.

Papule = solid palpable inflammatory lesion \leq 5mm diameter

Pustule = pus-filled inflammatory lesion \leq 5mm in diameter

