8. STATISTICAL ANALYSIS

The sections that follow highlight sample size determination and the planned analyses for this study. A statistical analysis plan (SAP) will be prepared separately from this protocol which gives descriptions of the statistical methods, models, hypotheses and subject populations to be analyzed. The SAP will be completed and approved before locking the database and unblinding the study and will serve as a companion to the protocol and the *de facto* documentation of the proposed statistical evaluation. The SAP will be completed and finalized prior to breaking the blind.

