### 5.3 Demographics and Baseline Characteristics

Baseline variables (e.g., sex, age, ethnic origin) will be evaluated, adjusting for site, to identify differences between treatment groups, which were not eliminated by randomization. Any significant baseline differences will be reviewed for their potential impact on the efficacy findings.

Continuous variables at baseline will be examined by two-way analysis of variance (ANOVA) with treatment and site as fixed effects when normal error and homogeneous variance assumptions are satisfied, or by the nonparametric rank based ANOVA when they are not, to compare treatment group differences.

Categorical variables such as gender, race, etc., will be examined by Cochran-Mantel-Haenszel test, stratified by site.

Summary tables by treatment group will be presented. For each continuous variable, the summary will include the mean, standard deviation, minimum and maximum. For each categorical variable, the summary will include frequencies and percentages.

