#### Equivalent Efficacy

For the mean percent change from baseline in the inflammatory lesion counts, the Test treatment will be considered to be therapeutically equivalent to the Reference treatment if the 90% confidence interval on the Test-to-Reference ratio of means, calculated by Fieller's Method, falls within the interval 0.80 to 1.25. The compound hypothesis to be tested for therapeutic equivalence between test and reference is:

$$H_0: \mu_T / \mu_R \leq 0.80 \text{ or } \mu_T / \mu_R \geq 1.25 \text{ versus}$$

$$H_A: 0.80 < \mu_T / \mu_R < 1.25.$$

Where  $\mu_T$  and  $\mu_R$  are the mean percent change from baseline to Week 12 (Visit 4/Day 84) in inflammatory lesions counts for the test treatment and the reference treatments, respectively. The null hypothesis is rejected when the two-sided 90% confidence interval (CI) for the ratio of means between test and reference products is between 0.80 and 1.25. Rejection of the null hypothesis supports the conclusion of therapeutic equivalence between test and reference products for the primary efficacy variable.

The two-sided 90% confidence interval will be constructed using an ANOVA model adjusting for the effects of treatment and site. A skewness test (SAS® PROC UNIVARIATE) will be performed using the residuals from the ANOVA of the primary efficacy variable. If the skewness statistic is less than -2, the analysis will be performed on the ranked mean percent change from baseline to Week 12 (Visit 4/Day 84) in inflammatory lesion counts.

The same analysis will be applied to the mean percent change from baseline in the non-inflammatory lesion count.

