#### Superiority

Evaluation of superiority will be conducted separately for the Test versus Placebo products and for the Reference versus Placebo products comparing their difference in the percent change from baseline in the inflammatory lesion counts using ANOVA with treatment and site as fixed effects. If the mean percent change for an active treatment is greater and statistically different (two-sided,  $p < 0.05$ ) than that of the Placebo, then the active treatment will be considered superior to the Placebo. The compound hypothesis to be tested for superiority of test and reference over Vehicle is:

$H_0: \mu_T \leq \mu_V$  or  $\mu_R \leq \mu_V$  versus

$H_A: \mu_T > \mu_V$  and  $\mu_R > \mu_V$

Where  $\mu_T$ ,  $\mu_R$  and  $\mu_V$  are the mean percent change from baseline to Week 12 (Visit 4/Day 84) in inflammatory lesions counts for the test, the reference and the vehicle treatments, respectively.

. The null hypothesis is rejected when both p-values from the ANOVA are less than 0.05 (two-sided test). Rejection of the null hypothesis supports the conclusion of superiority of active product over the vehicle product for the primary efficacy variable.

[REDACTED]

The same analysis will be applied to the mean percent change from baseline in the non-inflammatory lesion count.

[REDACTED]

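### The co-primary lesion-count models adjust for treatment and centre but not for the recorded baseline count, giving up a cheap, probably small gain in precision

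*Protocol*

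**What the plan says.** Protocol 8.1.4 judges equivalence by whether Fieller's 90% interval for the Test-to-Reference ratio lies within 0.80 to 1.25. The means and residual variance for that interval "will come from an Analysis of Variance of the Test and Reference results using a statistical model containing terms for Treatment and Center". Superiority of each active arm over Vehicle is tested "via an Analysis of Variance using a statistical model containing terms for Treatment and Center".

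SAP 5.5.1 agrees. For equivalence: "The two-sided 90% confidence interval will be constructed using an ANOVA model adjusting for the effects of treatment and site". For superiority, the comparison is made "using ANOVA with treatment and site as fixed effects". Both analyses are extended to the non-inflammatory count.

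The baseline counts are available. Protocol 5.9.1 says that inflammatory lesions "are to be counted at baseline and at each subsequent visit", and 5.9.2 says the same of non-inflammatory lesions.

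On baseline imbalance, SAP 5.3 says: "Baseline variables (e.g., sex, age, ethnic origin) will be evaluated, adjusting for site". It then says: "Any significant baseline differences will be reviewed for their potential impact on the efficacy findings". No adjusted analysis is named there or in Protocol 8.2.

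**The concern.** Residual variance from the treatment-plus-centre model sets the width of the interval that decides equivalence. Any part of it that the baseline count could explain widens that interval and also lowers power against Vehicle, on both co-primary endpoints.

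Percent change already divides by baseline. Division does not guarantee that percent change is unrelated to baseline, and only the remaining association is at issue here.

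To the extent of that association, a chance difference in baseline counts between Test and Reference also carries into the unadjusted ratio. The legible plan answers this with significance tests and a later review, so any adjustment would be chosen after the results are known. A covariate named now removes that discretion.

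**Working it through.** **Model terms.** The four legible model statements (protocol and SAP, equivalence and superiority) each list treatment and centre or site, and nothing else.

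**Inputs.** The documents give the 90% interval, the 0.80 to 1.25 limits, Fieller's method and two-sided 0.05 for superiority. Sample size, allocation, SD and correlation are not legible, so there is no planned figure to reproduce and everything else is assumed:
- rho, the correlation of baseline count with percent change within treatment and centre: 0 to 0.3
- mean reduction 55 and SD 40, so SD/mean = 40/55 = 0.73, with 0.6 and 0.9 as alternatives
- equal Test and Reference arms of 150 to 400
- true ratio 1

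**1. Interval width.** The residual SD is multiplied by sqrt(1 - rho²), so the narrowing is 1 - sqrt(1 - rho²). For rho 0.1, 0.2 and 0.3 this is 1 - sqrt(0.99) = 0.50%, 1 - sqrt(0.96) = 2.02% and 1 - sqrt(0.91) = 4.61%.

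**2. Equivalence power, one endpoint.** The two one-sided 5% tests use
- (xT - 0.8 xR) / (s sqrt(1.64/n)), where 1.64 = 1 + 0.8²
- (xT - 1.25 xR) / (s sqrt(2.5625/n)), where 2.5625 = 1 + 1.25²

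Hand check at n = 200, rho 0: 11/(40 × sqrt(1.64/200)) = 11/3.622 = 3.04, and 13.75/(40 × sqrt(2.5625/200)) = 13.75/4.528 = 3.04. Each test passes with probability Φ(3.037 - 1.645) = 0.918, so joint power is about 2 × 0.918 - 1 = 0.836. This agrees with the simulated 83.4%. Results from 1,000,000 draws:

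| n per arm | SD/mean | rho 0 | 0.1 | 0.2 | 0.3 |
|---|---|---|---|---|---|
| 150 | 0.73 | 67.2% | 67.9% | 69.8% | 73.1% |
| 200 | 0.73 | 83.4% | 83.9% | 85.3% | 87.5% |
| 300 | 0.73 | 96.2% | 96.3% | 96.8% | 97.5% |
| 400 | 0.73 | 99.2% | 99.2% | 99.4% | 99.6% |
| 200 | 0.6 | 95.7% | 96.0% | 96.5% | 97.3% |
| 200 | 0.9 | 58.0% | 58.6% | 60.8% | 64.4% |

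**3. Superiority power.** New power = Φ((z0.975 + z_power)/sqrt(1 - rho²) - z0.975). For rho 0.1, 0.2 and 0.3, 80% becomes 80.4%, 81.6% and 83.6%, and 90% becomes 90.3%, 91.1% and 92.5%.

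**4. Chance imbalance.** At 200 per arm, the standard error of the baseline difference is sqrt(2/200) = 0.10 SD. A two-standard-error difference of 0.2 SD shifts the unadjusted ratio by about rho × 0.2 × 0.73, which is 0.015, 0.029 and 0.044 at rho 0.1, 0.2 and 0.3.

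**5. The proposed analysis, simulated.** The check used 40,000 trials, 200 per arm, 12 unequal centres (2 to 45 per arm), a skewed baseline, size-weighted centres, both means taken at the pooled baseline mean, and their full covariance.

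| rho | Power, unadjusted | Power, adjusted | Interval narrowing |
|---|---|---|---|
| 0 | 83.4% | 83.3% | -0.13% |
| 0.05 | 83.4% | 83.4% | 0.00% |
| 0.1 | 83.4% | 83.7% | 0.39% |
| 0.2 | 83.1% | 84.8% | 1.93% |
| 0.3 | 83.6% | 87.3% | 4.56% |

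At a true ratio of 0.80, both models declared equivalence in 4.9% to 5.2% of trials, so type I error is held.

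**6. Likely rho.** Simulated percent change from overdispersed counts, with an assumed entry minimum of 20 lesions, gave an absolute rho of 0.06 to 0.21.

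**7. What a ratio of adjusted means needs.**
- *Reference baseline value.* Take adjusted means of 46 and 55 (ratio 0.836), SD 40 and rho 0.2. Half a baseline SD moves each mean by 0.2 × 40 × 0.5 = 4, so the ratio becomes 42/51 = 0.824 or 50/59 = 0.847.
- *Centre weights and covariance.* In the planned model without a covariate, with the same 12 centres, the two least-squares means correlate 0.41 under equal centre weights and 0 under size weights. With equal weights and an observed ratio of 1, Fieller's interval is 0.886 to 1.128 with the covariance and 0.855 to 1.170 if it is set to zero.

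**The case against.** The strongest reply is that this is a preference. The planned model is valid and pre-specified, and baseline is already the divisor. In the simulated range of rho (0.06 to 0.21) the interval narrows by only 0.2% to 2.2%. No input comes from the trial, and at 400 per arm power already exceeds 99%. All of this stands, and it is why the point is a recommendation about efficiency.

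Chance imbalance is also already covered by the interval's stated confidence level. That is correct: it is not bias, and its size depends on the same rho. What remains is that the legible plan names no adjustment in advance. The baseline variables in SAP 5.3 are only examples, so lesion counts may well be tested, but testing them does not adjust the ratio.

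The fix adds a choice that the planned model does not need, the baseline reference value, and step 7 shows that it matters near the limit. Naming one value before unblinding settles this. Centre weights and covariance are questions for the planned model as well, and they add no weight to the present point.

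SAP 5.5.1 has a rank-based fallback for skewed residuals, and the fix does not cover it. Redacted text may hold a supportive analysis. The protocol also cites product-specific bioequivalence recommendations that cannot be seen here. These limits lower confidence, but the legible statements of the primary model are complete in themselves.

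**Conclusion.** The concern holds as a recommendation. Both documents omit the baseline count from the equivalence and superiority models for both co-primary endpoints, although the count is collected. Type I error is not affected.

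The gain is unknown and probably small: 0% to about 4.6% off the interval width for rho up to 0.3. At 200 per arm and SD/mean 0.73, that is at most about 4 points of equivalence power. It is worth most if power is marginal (58% to 64% at SD/mean 0.9 and rho 0.3) and almost nothing if the trial is large or rho is below about 0.05. All of these sizes rest on assumed rho, SD/mean and arm size, with a true ratio of 1.

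**What to change.** The protocol leaves room for the change: "The SAP will be completed and finalized prior to breaking the blind". Before then:

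- Add the baseline count of the same lesion type to the equivalence and superiority models, so that the terms are treatment, site and baseline count.
- For Fieller's method, evaluate both adjusted means at one named baseline value: the pooled Test and Reference mean in the population analysed (PP or mITT).
- State the centre weights, for example proportional to the number of Test and Reference subjects in each centre.
- Use the full covariance matrix of the two means.
- Report the planned unadjusted ANOVA as a sensitivity analysis.

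The cost is one model term, a sentence each for the reference value and the weights, one degree of freedom, and an assumed linear baseline effect. No new data are needed, and the sensitivity analysis shows whether the linearity assumption matters.

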8.1.5 Safety and Adverse Events Analysis

The frequency and percent of subjects with adverse events will be summarized by MedDRA system organ class and preferred term and by severity and relationship to study drug for all three treatment groups. The adverse events reported by at least five percent of the subjects in any treatment group will also be tabulated. The comparable safety of the Test and Reference

[REDACTED]

treatments will be evaluated by statistical comparison of the proportion of subjects who reported any adverse events. The test and reference treatments' frequency and distribution of application site reactions of erythema, burning/stinging, erosion, edema, pain and itching will be summarized and compared descriptively. Safety comparisons will be performed only for the safety intent-to-treat population.

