2.2 Safety

Safety of the test and reference products will be compared by evaluating the nature, severity and frequency of their adverse event profiles. All adverse events that occur during the study will be recorded. Descriptions of reactions or complaints will include the approximate date of onset, the date the adverse event ended, the severity of the adverse event, and the outcome. Comparisons between the treatment groups will be made by tabulating the frequency of Subjects with one or more adverse events (classified into MedDRA terms) during the study. Pearson's Chi-Square test or Fisher's Exact test, whichever is most appropriate, will be used to compare the proportion of subjects in each treatment group with any adverse event. The adverse events reported by at least five percent of the subjects in any treatment group will be summarized descriptively.

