5.10 Application Site Reaction Assessment

At baseline and each subsequent visit, application site reactions such as erythema, dryness, burning/stinging, erosion, edema, pain and itching are to be recorded. Pain and itching symptoms will be assessed by discussion with the subject and will be reported as the severity experienced within 24 hours of the trial visit.

The Application Site Reaction Assessment must be conducted by qualified investigators listed on the Form FDA 1572 who have been delegated these tasks by the PI. [REDACTED]

[REDACTED]

[REDACTED]

Application site reactions are not to be recorded as adverse events unless they result in either:

- The temporary discontinuation of the study medication.
- The discontinuation of the subject from the study.
- The use of a new concomitant medication in order to treat this event.

Site Reaction	DESCRIPTION
Erythema	[REDACTED]
Dryness	[REDACTED]
Burning/Stinging	[REDACTED]
Erosion	[REDACTED]
Edema	[REDACTED]
Pain	[REDACTED]
Itching	[REDACTED]

SCORE	ASSESSMENT	DESCRIPTION
0	None	Absent
1	Mild	Slight, barely perceptible
2	Moderate	Distinct presence
3	Severe	Marked, intense

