#### Adverse Events

Adverse events (AEs) will be coded in MedDRA, version 14.0 or higher. Treatment-Emergent Adverse Event (TEAE) is defined as any AE occurs on or after applying the first dose of study drug. Number and percent of subjects reporting TEAEs will be tabulated by treatment group. Summaries will be presented by body system and preferred term for the ITT population. Similar tables will be presented by severity and relationship to study drug. TEAEs reported by 5% or more subjects for any treatment group will also be summarized. In summaries of incidence rates (frequencies and percentages), severity and relationship to study drug of individual, subjects who report more than one event that are mapped to the same preferred term will be counted only once under the strongest severity and relationship, accordingly. The difference between Test and Reference treatments with regard to the severity and frequency of their dermatological adverse events will be statistically evaluated. Fisher's exact test will be used to compare the proportions of subjects of the two active treatment groups who report any TEAE.

Treatment-Emergent Serious Adverse Events (TESAEs) and TEAEs that led to treatment interruption or discontinuation will be presented in data listings.

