#### Application Site Reactions

Frequency and distribution of application site reactions of erythema, dryness, burning/stinging, erosion, edema, pain and itching will be summarized and compared descriptively by visit.

Safety comparisons will be performed only for the ITT population.

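### Test–Reference safety comparability is tied to a test of no difference with no interval planned in the visible text, and such a test cannot by itself support it

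*Protocol*

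**What the plan says.** Comparing the safety profiles of Test and Reference is part of the stated objective (Protocol 2; SAP 2). Protocol 8.1.5 names the aim and the tool in one sentence: comparability on safety "will be evaluated by statistical comparison of the proportion of subjects who reported any adverse events".

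The SAP (5.6, Adverse Events) makes this specific: "Fisher's exact test will be used to compare the proportions of subjects of the two active treatment groups who report any TEAE". Protocol 2.2 is a little wider: "Pearson's Chi-Square test or Fisher's Exact test, whichever is most appropriate, will be used". Tests are two-sided at 0.05 (SAP 5.1).

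Other safety comparisons are planned:

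- The SAP says that the Test–Reference difference "with regard to the severity and frequency of their dermatological adverse events will be statistically evaluated". It names no method.
- Application site reactions are handled descriptively. In Protocol 8.1.5 they "will be summarized and compared descriptively. Safety comparisons will be performed only for the safety intent-to-treat population"; in the SAP, "erosion, edema, pain and itching will be summarized and compared descriptively by visit".
- AEs are "summarized by MedDRA system organ class and preferred term and by severity and relationship to study drug for all three treatment groups" (Protocol 8.1.5), with a further table at the 5% threshold.
- Serious TEAEs, and TEAEs leading to interruption or discontinuation, are listed (SAP 5.6).

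Protocol 5.10 limits what reaches the any-AE count: "Application site reactions are not to be recorded as adverse events unless they result in either" a temporary stop of study medication, discontinuation from the study, or a new concomitant medication.

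**The concern.** Fisher's test takes no difference as its null hypothesis. Failing to reject that null does not show that two products are alike, and sparse data make failure more likely. A p-value also does not tell the reader how large an excess of AEs on Test the data still allow.

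Elsewhere the plan uses the right logic. Efficacy equivalence is judged by 90% confidence intervals: against 0.80 to 1.25 for the lesion counts, and against −20% to +20% for IGA success, which is a difference of two proportions just as the any-AE comparison is (Protocol 8.1.4; SAP 5.5). The safety comparison has no corresponding interval in the visible text.

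What is at stake is the safety half of the Test–Reference objective. A report could state the AE proportions and a p-value above 0.05 and leave the reader without the one figure that bears on comparability.

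**Working it through.** **Step 1: is there a figure to reproduce?** No. Sample size and allocation are blacked out, and no expected AE rate, safety margin or safety power is given. All arm sizes and rates below are assumptions, for illustration only.

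**Step 2: the point that needs no assumption.** Suppose the two arms are equal in size and show the same number of subjects with a TEAE. The two-sided Fisher p-value is then 1 at any sample size. The interval for the difference is centred on zero, but its width depends on n:

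half-width = z × √(2p(1 − p)/n), with z = 1.96 (95%) or 1.645 (90%).

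For p = 0.10 and n = 150: √(2 × 0.10 × 0.90/150) = √0.0012 = 0.0346. This gives 1.96 × 0.0346 = 6.8 points and 1.645 × 0.0346 = 5.7 points. For n = 500: √0.00036 = 0.0190, giving 3.7 and 3.1 points.

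| n per active arm | 150 | 200 | 300 | 400 | 500 |
|---|---|---|---|---|---|
| 10% in both arms, 95% half-width (points) | 6.8 | 5.9 | 4.8 | 4.2 | 3.7 |
| 10% in both arms, 90% half-width | 5.7 | 4.9 | 4.0 | 3.5 | 3.1 |
| 20% in both arms, 90% half-width | 7.6 | 6.6 | 5.4 | 4.7 | 4.2 |

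So the same p-value goes with an upper limit on the excess that nearly halves across this range. Only the interval shows that.

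**Step 3: how often would a true excess be non-significant?** Exact power of the two-sided 0.05 Fisher test is the sum, over all pairs of counts (x, y) with Fisher p ≤ 0.05, of Bin(x; n, p_R) × Bin(y; n, p_T), with equal arms.

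| Reference v Test | 150 | 200 | 300 | 400 | 500 |
|---|---|---|---|---|---|
| 5% v 10% | 0.30 | 0.41 | 0.59 | 0.74 | 0.83 |
| 10% v 15% | 0.21 | 0.28 | 0.41 | 0.53 | 0.64 |
| 20% v 25% | 0.15 | 0.19 | 0.28 | 0.36 | 0.44 |
| 10% v 20% | 0.63 | 0.77 | 0.92 | 0.98 | 0.99 |
| 20% v 30% | 0.47 | 0.60 | 0.78 | 0.89 | 0.95 |

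A true 10% v 15% would be missed in 79% of trials at 150 per arm (1 − 0.21) and 36% at 500 (1 − 0.64). A true 10% v 20% would be missed in 37% at 150 and 1% at 500.

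**Step 4: do the other planned outputs fill the gap?** The AE tables give counts and percentages without a measure of uncertainty. The dermatological evaluation has neither a named method nor a planned interval. Site reactions are compared descriptively. Under Protocol 5.10 they count as AEs only if they lead to one of the three listed consequences. The any-AE test therefore leaves out every site reaction below that threshold, probably most of them, though the documents give no rates.

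**The case against.** **Fisher's test is not the only safety evidence.** A reader might infer that it is, but the documents do not support that. The SAP sentence just before the Fisher sentence plans a second Test–Reference evaluation, of dermatological AEs. The AE tables, listings and site-reaction comparisons come on top. This stands. What remains is that Fisher's is the only inferential method the SAP names for the comparison, and that no output has a planned interval for the difference.

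**No decision rule is stated.** A reader might also infer that p ≥ 0.05 will be read as proof of comparability. Neither document says so. Efficacy has an explicit rule for declaring equivalence; safety has none, and Protocol 2.2 frames the comparison as one of the nature, severity and frequency of AEs. This stands too. But Protocol 8.1.5 does tie comparability to this test, so the plan should say how a non-significant result is to be read.

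**Low power cannot be established.** Arm sizes, AE rates and the difference of interest are all unknown. A 5-point excess is poorly detected over most of the assumed range, but 5% v 10% reaches 83% at 500 per arm and 10% v 20% reaches 92% at 300. Calling the test low-powered as a fact would go beyond the documents. The point does not depend on it.

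**The information is not lost.** Counts and percentages by arm are tabulated, so the observed difference is visible and an interval can be derived from them. That is true; what is missing is the preplanned row and its stated use.

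**An interval without a margin proves nothing either.** This is also right, so the interval should be offered as an estimate of the excess still possible, not as a pass/fail test.

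**Redaction.** Safety text is blacked out in the Protocol synopsis, so the absence of an interval can be claimed only for the visible text.

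**Conclusion.** The concern holds in a limited form. The formal Test–Reference safety comparison is a test of no difference without a planned interval in the visible text, and a non-significant result cannot by itself support comparable safety at any sample size. The documents do not show that this test is the sole safety evidence, that non-significance will be taken as comparability, or that power is low.

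The size of the gap can only be illustrated. At an assumed 150 to 500 per active arm, with equal arms and 10% on Reference, Fisher power is 21% to 64% against a 5-point excess and 63% to 99% against a 10-point excess. With 10% in both arms, the 95% half-width runs from 6.8 to 3.7 points and the 90% half-width from 5.7 to 3.1.

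No efficacy conclusion is affected, and safety is not among the primary or secondary endpoints in Protocol 2.1. The change is still worth making, because the safety comparison is a stated objective and the better method is nearly free.

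**What to change.** In SAP 5.6, mirrored in Protocol 8.1.5:

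- Report the Test minus Reference difference in the proportion of subjects with any TEAE, and with TEAEs leading to interruption or discontinuation, each with a two-sided confidence interval (for example Miettinen–Nurminen).
- State the level. Protocol 8.1.4 sets confidence intervals at 90%, so use 90% to match, or 95% declared as an exception.
- Use the same estimate and interval for the dermatological AE comparison, which now has no named method.
- Base the safety statement on the estimate and the upper limit of the excess. Keep Fisher's p-value as supportive, and state that p ≥ 0.05 is not evidence of comparable safety.

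This costs some SAP and protocol wording and a few table rows, with no new data collection. The downside for the sponsor is that a wide interval may make the safety statement less favourable.
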